CLINICAL STUDY PROTOCOL

Interventional Drug or Biologic

Sympathetic activation in obesity

Protocol Number

2000030749

Protocol Version

03/14/2022

Version #2

PRINCIPAL INVESTIGATOR:

Name [name]

Department Internal Medicine / Section of Endocrinology

[contact]

Email Address [contact]

IND Number:

IND Holder:

NCT Number: NCT04946552

Study Phase (1, 2, 3, or 4-postmarketing):

Confidentiality Statement:

HIC 2000030749

REVISION HISTORY:

Revision #	Version Date

HIC 2000030749

Synopsis

Primary Objective

The primary objective of this study is to determine whether sympathetic nervous system (SNS) activity in adipose tissue (WAT and BAT), muscle and brain is altered in individuals with obesity in comparison to individuals with normal weight. Simultaneous multi-organ SNS activation will be obtained with a radiotracer for norepinephrine transporters (NET) for whole-body Positron Emission Tomography in combination with low dose computed tomography (PET/CT) imaging and microneurography (gold standard test for assessment of muscle SNS activity).

Secondary Objective (if applicable)

The secondary objectives of this study are: 1) to evaluate whether gender differences affect peripheral SNS in healthy normal weight and obese men and women in adipose tissue (WAT and BAT) and muscle (resting/fasting); 2) To investigate the relationship between peripheral and central SNS activity in obesity, by correlating SNS activity in peripheral tissues (WAT, BAT, and muscle) and brain; and 3) To investigate NET CNS and peripheral SNS activity before and after a high carbohydrate mixed meal in lean and obese men and women.

Study Duration

4 years

Study Design

Aim: To measure peripheral SNS in healthy normal weight and obese men and women in adipose tissue (WAT and BAT), deltoid skeletal muscle, and brain NET at fast and after a mixed meal test (MMT).

The goal of this study is to measure in 20 individuals with normal weight (BMI 18-25 kg/m²) and 20 individuals with obesity (BMI 30-50 kg/m²) NET-binding in WAT and BAT to better understand the role of SNS in obesity. SNS activation of a) peripheral tissues: adipose tissue (BAT and WAT) and skeletal muscle; and b) CNS NET will be measured synchronously by using [¹¹C]MRB whole body PET/CT imaging in combination with the gold standard measurement of peripheral SNS activity (muscle sympathetic nervous activity (MSNA)).

Visit 1 - Screening procedures:

Potential subjects will complete pre-screening over the telephone to determine preliminary eligibility based on inclusion/exclusion criteria and basic socio-demographic information will be collected. Potentially qualifying participants will then be screened in person at the Yale New Haven Hospital (YNHH) Research Unit (HRU) or Church Street Research Unit (CSRU) with vital signs, EKG, a medical history and physical exam. Fasting blood will be collected for HbA1C, creatinine, liver enzymes (ALT, AST), TSH, hematocrit, and lipid panel. A urine pregnancy test will be administered.

Oral glucose tolerance test (OGTT) will be administered as follows: Following a 10-hour overnight fast, a nurse will insert an intravenous (IV) catheter. Subsequently, subjects will ingest 7.5 oz of Glucola, which contains 75 g of dextrose in orange flavored water. Blood samples will be taken at -

HIC 2000030749

15, 0, 10, 20, 30, 60, 90 and 120 minutes (after glucola ingestion) for the measurement of plasma glucose, insulin, and C-peptide concentrations, and calculation of measurements of insulin sensitivity index (Matsuda Index). Approximately 40 mL of blood will be drawn at this visit.

Body Composition, Percent Body Fat & Percent Body Water: will be assessed using bioelectrical impedance analysis Tanita® scale (FDA cleared); which is a special multi frequency segmental body composition analyzer that delivers a very mild electrical current that allows measurement of fat mass, percent body fat, fat free mass, total body water, and percent body water. This test will be performed at screening visit. For better accuracy, measurement of percent fat and percent body water will be obtained with whole body Dual X-Ray Absorptiometry (DXA) scan (Hologic®) (located in the HRU) on screening-OGTT visit. The scanner arm will move over the participant's body from feet to head. The machine uses a small amount of radiation (one tenth of the amount of radiation from a chest x-ray) to measure body fat, muscle and bone density.

Visit 2 – Whole body PET/CT Imaging Visit - FASTING:

Two weeks after the screening visit, participants who qualified for the study will be asked to come to the PET Center to undergo the whole body [¹¹C]MRB PET scan. Participants will be asked to maintain their regular exercise routine.

Human PET-CT Protocol: [¹¹C]MRB will be synthesized at the Yale PET center based on procedures described and previously performed ^{1,2}. An intravenous bolus dose of MRB (~20mCi) will be injected by an infusion pump. PET data will be acquired dynamically for 120 min using the Siemens mCT-X whole-body PET/CT scanner using continuous bed motion to image perform multiple PET bed acquisitions from the top of the head to the lower abdominal region. A CT scan will be performed for attenuation correction and to help delineate the BAT and other regions of interest (ROIs). Images will be reconstructed with an ordered subset expectation maximization algorithm using point spread function correction and time-of-flight information. To delineate fat (WAT, BAT) and skeletal muscle regions of interests (ROIs), CT images are first resliced to match the resolution and location of PET images. As performed in previous studies ², a supraclavicular ROI is first manually drawn on the CT images. Within that area, the fat ROI is segmented using the CT images and an intensity window from -200 to -50 HU. Subsequently the fat ROI is segmented into WAT and BAT ROIs by using the ¹¹C-MRB PET images: Standardized Uptake Value (SUV) \geq 1.25 for BAT, SUV $<$ 1.25 for WAT. Brain ROIs for predetermined NET-rich areas of the brain, including the locus ceruleus, raphe, thalamus and hypothalamus were defined in template space and are applied to the PET images by using the participant's MR image as an intermediate step. For analysis of tracer uptake, mean SUV will be reported for segmentation of adipose tissue. Because the distribution volume ratio (DVR) is a more precise measurement of uptake for reversible tracers ³ such as ¹¹C-MRB, regional quantification of ¹¹C-MRB uptake as DVR (V_T/V_{ND}), estimated via multilinear reference tissue model 2 (MRTM2) ^{4,5} ($t^*=30$ min) using the occipital cortex, a region with low NET density ^{2,5,6} as the reference region. MRTM2 reduces the variability of MRTM (4) parameter estimates by fixing one of the three parameters, the parameter k_2' , which is only related to the reference region time-activity curve, to a common value for all target regions. In this study, the parameter k_2' was fixed to 0.021 min⁻¹, based on previous brain studies and previous BAT PET studies ². In addition to DVR, MRTM2 can estimate R_1 , the relative radioligand delivery, using a 1 tissue compartment model (1TC). For

HIC 2000030749

the 1TC model, volume of distribution, $V_T = K_1/k_2$, where K_1 (mL/min⁻¹/mL⁻¹) is the rate constant of radiotracer from plasma to tissue of target organ and k_2 is the rate constant from tissue to plasma. Using a reference region with non-displaceable binding (e.g. occipital lobe) we can estimate similar rate constants: $V_{ND} = K'_1/k'_2$. Recalling that K_1 and K'_1 are the rate constants for transfer from plasma to the tissue and reference region, respectively, then we can estimate relative radioligand delivery as $R_1 = K_1/K'_1$.

Visit 3 – Whole body PET/CT Imaging Visit - High-Carbohydrate Mixed Meal Test (MMT)

High Carbohydrate Mixed meal test (MMT): Two weeks after visit 2, participants will come to the PET Center after a 10-hour overnight fast. A nurse will insert an intravenous (IV) catheter and subjects will ingest a liquid meal (65% CHO, 20% fat, and 15% protein, equal to 40% of daily energy expenditure, per ~16 ounces) to be prepared by the Metabolic Kitchen located at the HRU. Blood samples will be collected at -10, 0, 15, 30, 60, 90, and 120 min for measurement of glucose, insulin and C-peptide concentrations ⁷. Plasma samples will be drawn at baseline and throughout the MMT for measurement of additional hormones (such as leptin, ghrelin, thyroid hormones, and catecholamines) and free fatty acids (FFA) levels. Insulin and glucose will be used to calculate indexes of insulin sensitivity ⁷⁻⁹. Hormones, glucose and FFA will be correlated with PET measurements of brown fat at baseline and during the MMT. Approximately 60 mL of blood will be drawn at this visit.

Participants will undergo whole body [¹¹C]MRB PET scan as described in visit 3. After the MMT, PET data will be acquired dynamically for 120 min using the Siemens mCT-X whole-body PET/CT scanner after an intravenous bolus dose of MRB (~20mCi).

The order of the PET scan visits 2 and 3 will be randomized.

Measurement of Energy Intake: Hunger and fullness will be determined immediately before, during and after the PET scans with Visual Analog Scales (VAS).

Visit 4 – Sympathetic Nervous System Activity (SNSA) measurement Visit - Fasting

Two weeks after visit 3, participants will be asked to return for a separated visit for measurements of SNS activity at rest and fasting. This visit will be performed at the Pierce Laboratory ([name] laboratory). The participants will come in the morning (~9am) and will be asked to fast for 10-hour and to maintain their regular exercise routine. The following measurements will be obtained: MSNA, heart rate (HR), blood pressure (BP), electrocardiogram (EKG), and heart rate variability,. The proposed procedures will be performed at fasting (baseline). Participants will be asked to maintain their regular exercise routine.

Muscle sympathetic nerve activity (MSNA): Microneurography is the gold standard, most sensitive and reliable MSNA assessment in humans. The primary measure of sympathetic nervous system activity is peripheral nerve activity, as measured by MSNA.

HIC 2000030749

Muscle sympathetic nerve activity will be quantified by identification and measurement of sympathetic bursts in the integrated neurogram and expressed as burst frequency (number of bursts per unit time). ECG surface electrodes are applied to the chest, an elastic band incorporating a strain gauge element is strapped around the thorax for recording respiratory movements, and a sensor cuff of a servopulse-plethysmography arterial pressure monitor (FINAPRES, Ohmeda) is placed on the middle phalanx of the long finger (held at heart level). The experiments are carried out in an environmentally controlled chamber at an ambient temperature of 27.0 ± 0.1 °C. The experiment will begin with a 60-minute control period. During such time the subjects rest in the reclined position.

Measurements of HR, BP, and EKG (beat-to-beat) will also be obtained during the procedure. An intravenous catheter will be inserted into a forearm vein for blood sampling. Following the instrumentation period, resting HR, pulse interval (PI), BP, and MSNA will be recorded for 10 minutes. Following these measurements, plasma will be taken for measurements of insulin, glucose, free fatty acids, norepinephrine, and epinephrine levels. Approximately 20 mL of blood will be drawn at this visit. After the first blood sample and the 10-min rest phase, subjects will begin a seven-minute period of rest with paced breathing (12 breaths per minute) while HR, BP, PI and MSNA are measured. The subjects will synchronize breathing to a metronome set to a cadence of ~12 breaths per minute (0.2 Hz).

Procedure: Microneurography Recording of multiunit postganglionic muscle sympathetic nerve activity (MSNA) will be made from the common peroneal nerve as it winds around the fibular head with the subject in the supine position with the subject's thigh comfortably supported. This procedure requires us to first trace the course of the nerve using small electrical stimuli applied to the surface of the skin over the nerve or use the ultrasound to visually assist. This allows the microneurographer to find and focus the recording electrode tip on a nerve fascicle associated with muscle sympathetic activity. The time required to focus the electrode on the nerve averages about 30 min and will not exceed 60 min. In optimal conditions the track of the nerve from superficial stimulation is accurate and the nerve remains in position during insertion. An uninsulated subcutaneous electrode will serve as the reference. Mechanoreceptor afferent activity can be recorded during light tapping on the muscle belly or passive muscle stretch. A suitable intrafascicular recording site for MSNA consists of regular bursts and synchronous with the cardiac cycle. The neural activity is amplified (2x104), filtered (0.5-5.0 kHz), rectified, and integrated. The amplified and filtered nerve signal is also led to an audio monitor and through a resistance capacitance circuit (time constant 100 ms). The integrated nerve signal is digitized at 400 Hz along with the ECG signal while respiratory and arterial pressure signals are also sampled at 400 Hz (MacLab 8s). Data for analysis is selected from periods of quiet breathing in which subjects were relaxed and not talking. Microneurography was approved under HIC protocols # 8079, #0512000875, #1609018353 and is currently used under # 2000020950.

Cardiovascular variables. Recorded with a 16-channel computerized data-acquisition system at a sampling Speed of 400 Hz (ADI Instruments PowerLab 9, Castle Hill, Australia). Beat-to-beat DBP, SBP and pulse interval (PI) are determined using peak detection algorithms (44). Brachial artery BP and HR are measured with an automated sphygmomanometer (Colin Medical Instruments Corp,

HIC 2000030749

Komaki, Japan). Heart rate and pulse interval will be determined beat-to-beat from lead II of the EKG recording.

Visit 5 – Sympathetic Nervous System Activity (SNSA) measurement Visit – Mixed Meal Test (MMT)

Two weeks after visit 4, participants will be asked to return for a separated visit for measurements of SNS activity at rest and after intake of liquid meal. Participants will undergo similar procedures described on visit 4. However, MSNA will be obtained after MMT. The participants will come in the morning (~9am) and will be asked to fast for 10-hour and to maintain their regular exercise routine. A nurse will insert an intravenous (IV) catheter and subjects will ingest a liquid meal (65% CHO, 20% fat, and 15% protein, equal to 40% of daily energy expenditure, per ~16 ounces) to be prepared by the Metabolic Kitchen. Measurements of HR, BP, and EKG (beat-to-beat) will be obtained during the procedure. An intravenous catheter will be inserted into a forearm vein for blood sampling. Following the instrumentation period, resting HR, pulse interval (PI), BP, and MSNA will be recorded for 10 minutes. Following these measurements, plasma will be taken for measurements of insulin, glucose, free fatty acids, norepinephrine, and epinephrine levels. Approximately 40 mL of blood will be drawn at this visit.

Participants will be asked to maintain their regular exercise routine. The order of SNSA Fasting and MMT visits (visits 4 and 5) will be randomized. All study visits will be conducted within an 8-week period (including the two PET and SNSA scans).

Schematic figure of the visits and procedures to be done. The order of the PET scans will be randomized.

HIC 2000030749


Visit 1: Screening Visit
 
 -Review of Consent Form -Physical and Medical history review - Pregnancy Test (females) -EKG -Blood Work -OGTT -Body Composition 
 -Tanita Scale -DXA Scan 	
Visit 2: Whole body PET/CT Imaging Fasting Visit
 
 - Urine Pregnancy Test (females) - Urine Drug Screen - [¹¹C]MRB - Low dose CT scan and PET scan - Norepinephrine levels (serum) 
Visit 3: Whole body PET/CT Imaging Mixed Meal Test Visit
 
 - [¹¹C]MRB - Urine Pregnancy Test (females) - Urine Drug Screen - Ingestion of mixed meal - Measurement of Energy Intake - Low dose CT scan and PET scan - Norepinephrine levels (serum) 	
Visit 4: SNSA Visit – Fasting
 
 - BP, HR, PI, HR variability - EKG - MSNA 	
Visit 5: SNSA Visit - Mixed Meal Test
 
 - Ingestion of mixed meal BP, HR, PI, HR variability - EKG - MSNA

Abbreviations: BP=blood pressure, EKG=electrocardiogram, HR=heart rate, MSNA=Muscle sympathetic nerve activity, SNSA=Sympathetic Nervous System Activity
 
PET and MSNA visits do not need to occur in sequence, i.e. PET scans can occur before or after the MSNA.
			

Number of Study Sites
 
1
			

Study Population
 
We plan to enroll 20 participants with normal BMI (10 women and 10 men) and 20 with obesity (10 women and 10 men).
			

Number of Participants
 
40
			

Primary Outcome Variables
 
Primary outcomes: Group differences in 1) [¹¹C]MRB-binding in brown adipose tissue (BAT), white adipose tissue (WAT), skeletal muscle, and norepinephrine-rich brain regions (hypothalamus and thalamus); and 2) microneurography (muscle sympathetic nerve activity (MSNA)). Correlations between NET in the brain and peripheral NET and MSNA.
			

HIC 2000030749

Secondary and Exploratory Outcome Variables (if applicable)

Secondary endpoints: Plasma hormone levels, heart rate, blood pressure, and electrocardiogram (beat-to-beat). Correlations of secondary endpoints with NET in the brain and peripheral NET and MSNA.

HIC 2000030749

HIC 2000030749

Abbreviations

Abbreviation	Explanation
--------------	-------------

HIC 2000030749

Glossary of Terms

Glossary	Explanation
----------	-------------

HIC 2000030749

Table of Contents

Synopsis	3
Primary Objective	3
Secondary Objective (if applicable)	3
Study Duration	3
4 years	3

1.1 Introductory Statement

This document is a protocol for a human research study. The purpose of this protocol is to ensure that this study is to be conducted according to ICH GCP guidelines, and according to CFR 21 Part 312, other applicable government regulations and Institutional research policies and procedures.

HIC 2000030749

2 Background

2.1.1 Preclinical Experience

Obesity is one of the main drivers of insulin resistance, diabetes, and cardiovascular disease, and obesity-associated dysfunction of the sympathetic nervous system (SNS) may be implicated in the pathophysiology of these comorbidities ¹⁵⁻¹⁸. The SNS is integral to modulating energy homeostasis via activation of target organs, such as adipose tissue, skeletal muscle, liver, pancreas, and adrenal glands ¹⁹. However, this multi-organ SNS activation has been shown to be dysfunctional in obesity ^{20,21}. Central nervous system (CNS) noradrenergic neurons release norepinephrine (NE) in these target organs. NE recycling is a tightly regulated process modulated in large part by the norepinephrine transporter (NET) ²². Due to its important role in regulating NE signaling, NET has been considered a marker of noradrenergic system activity ²².

In humans, *in vivo* quantification of NET levels can be measured using a selective positron emission tomography (PET) radioligand for NET, (S,S)-¹¹C-O-methylreboxetine ([¹¹C]MRB) ^{23,24}, and our group has shown that [¹¹C]MRB can measure NET in multiple tissues including brown (BAT) and white adipose tissue (WAT), skeletal muscle, and brain ^{12,25}. Furthermore, our preliminary data using [¹¹C]MRB scanning in healthy lean individuals as well as individuals with obesity suggest that obesity is associated with marked differences in NET availability in BAT ² as well as the brain ²⁶. Use of PET allows us to assess NET binding in multiple tissues simultaneously. In these proposed studies, we will use NET-binding to investigate the role of SNS dysfunction in healthy men and women with obesity. Furthermore, because there is strong evidence that food induced SNS activity increment is blunted in individuals with obesity ^{15,27,28}, we will also test the impact of obesity on response to a relevant stimulus (food). Our overall premise is that **coordinated multi-organ response (brown and white adipose tissue, muscle, liver, pancreas) is modulated by the SNS both in the fasting state and after a meal; however, this coordinated response becomes dysfunctional in obesity**. Therefore, to better understand the potential for dysregulated coordination of the SNS in obesity, we will synchronously measure SNS activation of a) peripheral tissues: adipose tissue (BAT and WAT) and skeletal muscle; and b) CNS by using [¹¹C]MRB whole body PET imaging in combination with muscle SNS activity (MSNA) during rest both in the fasting state and after a meal.

[figure not shown]

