Human obesity is associated with altered brain NET. Central noradrenergic neuronal dysfunction has been observed in obesity ^{26,31-33}. Li et al ²⁶ demonstrated that obese subjects have decreased NET-availability in the thalamus (a sensory relay region in the brain); although these findings were not confirmed in a European cohort ³⁴. Vettermann et al ³⁵ showed that NET activity in the insula and hippocampus predicts successful weight loss. Furthermore, NET inhibitors used for the treatment of attention deficit disorder (ADHD) can promote weight loss ^{36,37}. In a prior study from our group ²⁵, we observed that NET in the hypothalamus correlated with counterregulatory hormonal and metabolic response to hypoglycemia (a stimulus to induce stress response

and increase hunger) ²⁵ (Figure 6). However, it is not clear whether NET- rich regions in the CNS,

HIC 2000030749

[figure not shown]
such as hypothalamus, thalamus, and brain stem (areas involved with glucose metabolism and autonomic function) are important in regulating SNS activation of target organs. We plan to investigate the relationship between CNS NET-availability and peripheral NET (measured by whole-body ($[^{11}\text{C}]$ MRB PET imaging) and SNS activity (measured by MSNA) both in normal BMI and obese individuals. We propose that CNS NET-availability at rest in the fasting state in the hypothalamus and thalamus (brain regions involved with glucose and energy metabolism) will correlate with NET binding in BAT and skeletal muscle in individuals with normal BMI. In contrast, because of obesity-associated regionalized SNS dysfunction, CNS-NET availability will not correlate with peripheral NET-binding or MSNA in individuals with obesity.

High carbohydrate meal ingestion is a strong stimulus for activation of the SNS. Food intake (in particular carbohydrate-rich meals) is a strong stimulus for activation of SNS in both animals³⁸ and humans³⁹⁻⁴². This has been demonstrated by plasma NE tracer kinetics^{38,39} and MSNA^{39,41-43}. In rodents, NE turnover in BAT, but not in the spleen or heart, increased in response to a meal³⁸. Regionalized SNS activation was also observed in humans: increased in skeletal muscle and kidneys, but no or minimal change in heart and liver³⁹. SNS play a major role in activating BAT after a meal⁴⁴, and a recent study using PET Imaging showed increased BAT activation after ingestion of a high carbohydrate-rich meal⁴⁵.

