2.2 Background/prevalence of research topic

Obesity affects more than a third of the population of the United States ⁴⁶ and carries an increased risk of developing type 2 diabetes, hypertension, heart disease, stroke, and certain types of cancers ⁴⁷. However, the exact mechanisms by which obesity contributes to these cardiometabolic disorders remains uncertain. Sympathetic nervous system (SNS) dysfunction has been described in individuals with obesity ¹⁵⁻¹⁸ and it has been proposed as one of the mechanisms involved in the development of obesity-related cardiometabolic complications ^{20,21}. It was initially proposed that obesity was associated with decreased SNS activity with a consequent decrease in energy expenditure and weight gain ⁴⁸. However, these findings were not confirmed by other reports. Some studies showed no change or even increased SNS activity (measured by plasma norepinephrine levels) ⁴⁹. Studies using microneurography, a direct measurement of SNS activation, showed that individuals with obesity may have sympathetic overactivity ^{17,18}. SNS activity may vary by tissue ^{21,50}. Specifically: SNS activation increases in kidneys and skeletal muscle and decreases or is unchanged in heart, and mostly unchanged in adrenal glands. Regionalized SNS hyperactivity in kidneys and skeletal muscle may lead to hemodynamic and metabolic changes in individuals with obesity. This results in an increased risk of developing hypertension and diabetes, and, in turn, cardiovascular morbidity and mortality. However, it is not exactly clear the interplay between obesity and regionalized SNS dysfunction. We propose that obesity is associated with dysfunctional coordination of SNS activation; and to prove that, we plan to measure synchronous SNS activity in various target organs in healthy individuals with normal body mass index (BMI) and with obesity.

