6.4 Statistical Method

6.4.1 Statistical Design

Primary endpoints: Group differences in 1) [¹¹C]MRB-binding in brown adipose tissue (BAT), white adipose tissue (WAT), skeletal muscle, and norepinephrine-rich brain regions (hypothalamus and thalamus); and 2) microneurography (muscle sympathetic nerve activity (MSNA)). Correlations between NET in the brain and peripheral NET and MSNA.

Secondary endpoints: Plasma hormone levels, heart rate, blood pressure, electrocardiogram (beat-to-beat)..

Statistical Analysis: Before statistical testing, all continuous variables will be tested for normality of distribution. Summary statistics will be computed. For between-group comparisons of patient characteristics, two sample t-test or Mann-Whitney U test will be used for continuous variables, and Fisher's exact test for categorical variables. Comparisons of repeatedly measured MSNA will be made using the mixed model analysis. Fixed factors include group and sex and their interactions. Linear contrasts comparing differences between groups or different time points within a group will be estimated.

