6.5 Planned Analyses

6.5.1 Primary Objective Analysis

The primary objective of this study is to quantify sympathetic nervous system (SNS) activity by [¹¹C]MRB PET imaging and microneurography (MSNA). [¹¹C]MRB binding will be quantified in adipose tissue (WAT and BAT), muscle; and whether [¹¹C]MRB binding and sympathetic bursts are altered in individuals with obesity in comparison to individuals with normal weight.

Statistical Analysis: Before statistical testing, all continuous variables will be tested for normality of distribution. Summary statistics will be computed. For between-group comparisons of patient characteristics, two sample t-test or Mann-Whitney U test will be used for continuous variables, and Fisher's exact test for categorical variables. Comparisons of repeatedly measured MSNA will be made using the mixed model analysis. Fixed factors include group and sex and their interactions. Linear contrasts comparing differences between groups or different time points within a group will be estimated.

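### The plan names no group-by-tissue test, no between-group test of the brain-periphery correlations and no BAT-WAT-muscle correlation, so it cannot support a conclusion that sympathetic dysfunction in obesity is regional or uncoordinated

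*Combined protocol and SAP*

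**What the plan says.** Section 2.1.1 gives the overall premise: organs respond to the sympathetic nervous system in a coordinated way, but "however, this coordinated response becomes dysfunctional in obesity". Section 4.1 repeats it as the hypothesis. Section 2.2 makes it the thing to be shown: "We propose that obesity is associated with dysfunctional coordination of SNS activation; and to prove that, we plan to measure synchronous SNS activity". Section 2.1.2 predicts that brain NET will correlate with BAT and muscle binding in normal-BMI participants. In obesity it predicts no correlation with peripheral binding or MSNA, "because of obesity-associated regionalized SNS dysfunction".

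The primary outcomes (Synopsis, 5.2, 6.4.1) are "Group differences in 1) [¹¹C]MRB-binding in brown adipose tissue (BAT), white adipose tissue (WAT), skeletal muscle, and norepinephrine-rich brain regions (hypothalamus and thalamus"), then MSNA, then correlations of brain NET with peripheral NET and MSNA. Section 6.5.2 lists the brain-periphery correlations again as a secondary objective.

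Section 6.5.1 names one model: "Comparisons of repeatedly measured MSNA will be made using the mixed model analysis". Its terms are limited: "Fixed factors include group and sex and their interactions". The t-test or Mann-Whitney sentence there covers patient characteristics, and no test is assigned to binding. Section 6.5.9 (Subsets and Covariates) is marked not applicable.

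**The concern.** A regional effect means that the lean-obese difference is not the same in every tissue. Loss of coordination means that organs covary less in obese than in lean participants. Each is a statement about a difference, and each needs a test of that difference.

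The plan supplies neither. A significant result in BAT beside a non-significant one in muscle does not show that the two effects differ. A significant correlation in lean participants beside a non-significant one in obese participants does not show that the correlations differ. The pilot already has the first pattern in women: P = 0.004 for BAT (6.4.2) and P = 0.088 for muscle (2.1.2). Coupling among BAT, WAT and muscle, which bears directly on multi-organ coordination, is not analysed at all.

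At stake is the study's main interpretive claim. Whether obesity alters binding in a given tissue can still be answered.

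**Working it through.** **Inputs from the documents.** 20 versus 20 participants (5.3.1). Five PET regions, three of them peripheral (6.4.1). BAT DVR 1.15 ± 0.19 lean and 0.80 ± 0.12 obese, two-sided t-test (6.4.2). Muscle P = 0.088 with 9 lean and 6 obese women (2.1.2).

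**Assumed, because the documents do not give them.** Alpha 0.05; normal data; the same standardised effect d in every tissue; between-tissue correlation rho of 0.3 to 0.7.

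**The plan's own figure.** d = (1.15 − 0.80) / √((0.19² + 0.12²)/2) = 0.35/0.159 = 2.20. Exact t-test power is 92.9% at 6 per group and 86.0% at 5. The plan's 6 and 5 per group are reproduced.

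**A second effect size.** For P = 0.088 on 13 degrees of freedom, t = 1.845. With a pooled t-test (assumed), d = 1.845 × √(1/9 + 1/6) = 0.97 for muscle.

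**Mixed significance under a uniform effect.** Each simulated trial was counted if at least one tissue, but not all, had p < 0.05. As an anchor with independent tissues, single-tissue power at d = 0.8 and 20 per group is 0.693. Five tissues then give 1 − 0.693⁵ − 0.307⁵ = 1 − 0.160 − 0.003 = 0.84, against 0.83 simulated. Results for rho 0.3 to 0.7, 20 per group:

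| True d in every tissue | Three peripheral tissues | Five regions |
|---|---|---|
| 0.5 | 35-56% | 48-73% |
| 0.65 | 38-61% | 52-79% |
| 0.8 | 34-52% | 47-69% |
| 0.97 | 23-33% | 31-45% |
| 1.5 | about 1% | 1-2% |
| 2.20 | about 0% | about 0% |

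Repeat runs differ by a point or two, so 33-61% is a fair summary for three tissues at d = 0.5 to 0.8.

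**Group-by-tissue test.** This was a Hotelling T² test on the tissue contrasts. It rejects in about 5% of trials when the effect is uniform on the scale analysed. With three tissues its power is 76-99% for effects (1, 0, 0), 25-51% for (0.5, 0, 0) and 17-35% for (0.8, 0.4, 0.4).

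**Correlations, 20 per group, Fisher z.** atanh(0.5) = 0.549.
- Within one group the standard error is 1/√17 = 0.243, so z = 2.26 and power is about 62%. If both groups truly have r = 0.5, exactly one is significant with probability 2 × 0.62 × 0.38 = 47%; direct simulation gives 46%.
- For the between-group difference the standard error is √(2/17) = 0.343. For r = 0.5 versus 0, z = 1.60 and power is about 36% (up to 38% by simulation).
- 80% power needs about r = 0.74 versus 0.

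**The case against.** Several points on the other side stand.

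The stated primary objective (4.2) is whether activity in these tissues is altered in obesity, and per-tissue differences answer that. The hypothesis in 4.1 speaks of dysfunctional coordination, not of unequal effects across organs. The regional wording comes from 2.1.2, where it explains a correlation prediction, and from 2.2, largely as a summary of earlier work.

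A reader might infer that the plan has no coordination analysis. It has one: the brain-periphery and brain-MSNA correlations sit among the primary outcomes. What is missing is a test that they differ between groups.

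A reader might also infer that a mixed pattern is the usual result of a uniform effect and will be reported as regional. The documents support neither part. The frequency depends on the effect size and is about 0% at the plan's d = 2.20. That value, however, is for BAT in women, and 6.4.2 itself allows for smaller differences in men. No passage says how a mixed pattern will be interpreted. Even tissue-by-tissue testing is inferred from the endpoint list, since no test is named for binding.

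Finally, a group-by-tissue test is no complete remedy. It compares means, so it says nothing about covariation. It also depends on scale: with assumed log-scale SDs in the ratio 1 : 0.5 : 0.75, an effect uniform in SD units is declared regional on the log scale in 11-15% of trials at d = 0.5 and 20-32% at d = 0.8. An effect uniform in percent terms keeps the error near 5%. BAT and WAT are separated at SUV 1.25 on the same PET images (5.1), so their contrast partly reflects the segmentation rule. These points shape the fix; they do not fill the gap.

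**Conclusion.** The concern holds in a limited form. The protocol sets out to show dysfunctional coordination and invokes regional dysfunction, but specifies no group-by-tissue test, no between-group test of the correlations and no BAT-WAT-muscle correlation. Neither conclusion could rest on the analyses as written.

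The chance of a misleading pattern is substantial if true effects are moderate, lower at the effect implied by the pilot muscle result, and negligible if every tissue shows the planning effect. For the correlations it is close to one in two when both groups share r = 0.5. These sizes rest on the assumed alpha, rho, normality and equal effects. The absence of the tests does not. This is a cheap improvement in answering the trial's own hypothesis, not a defect in the per-tissue comparisons.

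**What to change.** In 6.5.1:

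1. Add a repeated-measures model of fasting log DVR with tissue, group, sex and group-by-tissue terms and an unstructured covariance across tissues. State that a uniform effect means an equal percent difference.
2. Add two sensitivity analyses: one on standardised DVR, because the interaction depends on scale, and one without the BAT-WAT contrast.
3. State that a regional claim will rest only on the group-by-tissue term, not on which single tissues are significant.
4. State that a loss-of-coordination claim will rest on the between-group difference in correlations (brain-periphery, brain-MSNA and BAT-WAT-muscle). Estimate these separately by group, with confidence intervals, for example by Fisher z. One covariance pooled over groups cannot supply them.

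MSNA is in other units and comes from separate visits, so it stays outside the tissue factor.

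The cost is wording and a few analyses of data already collected. The downside to state openly is that both claims become harder to make and power is limited: about 17-35% for effects of 0.8, 0.4 and 0.4, and about 36-38% for r = 0.5 versus 0. A non-significant result would not show uniformity or intact coordination.
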